7.8.2 Laboratory data

Changes in coagulation and inflammatory markers on treatment, as outlined in [Section 5.3](#), are the laboratory parameters of special interest in this trial. They will be analysed in the efficacy section.

The analyses of laboratory data will be descriptive in nature and will be based on BI standards "Handling, Display and Analysis of Laboratory Data" ([12](#)).

The following laboratory parameters are considered safety and hence processed according to standard safety processing rules:

- Haematology (Haematocrit, Haemoglobin, Red blood cells (RBC) / Erythrocytes, White Blood Cells (WBC) / Leukocytes, Platelet Count / Thrombocytes)
- Clinical Chemistry (Albumin, Alkaline phosphatase, ALT (alanine transaminase), AST (aspartate transaminase), Bilirubin total, Creatinine, eGFR, Creatine kinase, Troponin, Lactate dehydrogenase, Glucose, Potassium, Sodium, Calcium, Magnesium, Urea (BUN), NT-proBNP)

For continuous safety laboratory parameters standardized values will be derived as well as the differences to baseline. Laboratory parameters will be shown in SI units.

Laboratory values will be compared to their reference ranges and frequency tables will be provided for the number of patients within and outside the reference range at baseline, each visit and the last measurement on treatment. Descriptive statistics will be provided by treatment group for baseline, each visit and last value on-treatment and for changes from baseline to each respective visit and last value on treatment. The laboratory parameters will be summarized by day of assessment.

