1.4.2 Risks

Bleeding events

Fibrinolytic treatment always harbours the risk of bleeding events. Depending on the anatomical location and severity of bleeding, the bleeding can be life threatening or even turn out fatal. The bleeding risk is potentially augmented when combining alteplase with anticoagulants or platelet inhibitor due to the combination of fibrinolysis, anticoagulation and/or platelet inhibition. The bleeding risk of alteplase also differs in relation to dose and rate. High doses of alteplase given at high rates increases bleeding risk. Low levels of fibrinogen ($<100 \text{ mg/dL}$) have also been identified to increase bleeding risk in relation to alteplase.

The bleeding risk can be partially estimated from the plasma level of fibrinogen. Due to its relative fibrin-specificity, alteplase results in a modest decrease of the circulating plasma fibrinogen levels to about 60% at 4 hours, which is generally reverted to more than 80% after 24 hours. Plasminogen and alpha-2-antiplasmin decrease to about 20% and 35% respectively after 4 hours and increase again to more than 80% at 24 hours [P86-5233]. A marked and prolonged decrease of the circulating fibrinogen level is only seen in few patients [P89-46753]. A plasma level of fibrinogen below 150 mg/dL has been associated with an elevated risk of bleeding [P13-13102]. The bleeding risk can be minimized by intensive monitoring of plasma fibrinogen levels and establishing stopping criteria or by dose reduction.

Vasculature health of the patient seem to play a major role in the bleeding risk. Confounding conditions affecting the vasculature health include high blood pressure, T2DM and advanced age. These conditions are considered patient-related risk factors for bleeding.

Alteplase administered intravenously carries a risk of bleeding and the extent of this risk is multifactorial (e.g. dose, weight, age, gender, blood pressure, diabetes) [P15-13160]. The highest number of bleeding events were seen in trials involving acute ischemic stroke patients, where the reported complications with alteplase total doses (up to 90 mg) given over

60 minutes were symptomatic intracerebral haemorrhage (6%) and other major haemorrhage (2%). Minor haemorrhage (e.g. bleeding at site of venepuncture) accounting for 20-25%.

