1.4.3 Discussion

Consideration of therapies that are not recognized for this indication but of potential benefit, such as fibrinolytic agents, is warranted in this unprecedented public health emergency of COVID-19.

The bleeding risk described in the literature typically include high dosages of alteplase (up to 90 to 100 mg given as infusion over 1-3 hours) and the concurrent use of therapeutic antithrombotics. However, the alteplase short-term infusion dosages being used in this study (0.3 mg/kg/2h or 0.6 mg/kg/2h) are lower than those used in studies for MI, massive PE and stroke. Additionally, by the low dose during long-term infusion over 12 hours, the rapid inactivation of alteplase in the circulation is projected to be associated with plasma fibrinogen levels well above the threshold of 150 mg/dL, which are known to be linked to the risk of bleeding [[c32479735-01; P13-13102](#)]. The safety results from Phase II (part 1) of the current trial were generally comparable across the treatment groups, except for bleeding events, which are a known side effect of alteplase. In Phase II, mainly non-major bleeding events were observed, and some of them were related to interventions. Additional risk minimization strategies to avoid intervention-related bleeding events have accordingly been implemented for Part 2, phase III of the study.

The bleeding risk is predicted from the plasma fibrinogen level which provides a measure of the alteplase absorbed. This will be monitored and if the level falls below 150 mg/dL, alteplase has to be temporarily interrupted. Beside the extent of fibrinogen breakdown, D-Dimer levels, thrombocytopenia, the prolongation of the activated partial thromboplastin time (aPTT) will be monitored continuously. Furthermore, elevated blood pressure as a risk of intracranial hemorrhage and the co-administration of ACE inhibitors related to the risk of angioedema will be monitored.

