5.2.3 Safety laboratory parameters

Safety laboratory parameters to be assessed are listed in [Table 5.2.3:1](#). For the sampling time points please see the [Flow chart](#). Local laboratory results will be used throughout the trial.

All analyses will be performed by the local laboratory, the respective reference ranges will be provided in the ISF. More details on collection of safety laboratory parameters are summarized in [Table 5.2.3:1](#)

Patients do not have to be fasted for the blood sampling for the safety laboratory.

Table 5.2.3:1 Safety laboratory tests

Haematology

• Haematocrit• Haemoglobin• RBCs / Erythrocytes• White Blood Cells (WBC) / Leukocytes• Platelet Count / Thrombocytes
Clinical chemistry

• Albumin*• Alkaline phosphatase*• ALT (alanine transaminase, serum glutamic-pyruvic transaminase [SGPT])• AST (aspartate transaminase, serum glutamic-oxaloacetic transaminase [SGOT])• Bilirubin total*• Creatinine (estimated GFR to be calculated according to local practice)• Creatine kinase (CK) *• Troponin I or T*• Lactate dehydrogenase• Glucose*• Potassium• Sodium• Urea (BUN) *• Type B natriuretic peptide (BNP), or NT-proBNP*
Coagulation and Inflammation

• aPTT (Activated partial thromboplastin time; in patients receiving UFH)• Prothrombin time, (or alternatively INR)• D-Dimer• Fibrinogen• Antithrombin*• Anti-Xa (in patients receiving LMWH)• C-reactive Protein• Procalcitonin*• Interleukin-6*• Plasminogen activator inhibitor 1*• Thrombomodulin*• Ferritin*

*If available locally

Clinically relevant abnormal findings as judged by the investigator will be reported as adverse events (please refer to [Section 5.2.6.1](#)).

5.2.4 **Electrocardiogram**

The 12-lead ECGs must be administered by a qualified personnel and results will be recorded as scheduled in the [Flow chart](#). The investigator or a designee will evaluate whether the ECG is normal or abnormal and assess clinical relevance. ECGs may be repeated for quality reasons and a repeated recording may be used for evaluation. In addition to the scheduled ECGs, ECGs should be done and documented at any time of clinical event (e.g. acute event of arrhythmia, tachy- or bradycardia, angina, or MI).

Dated and signed printouts of ECG with findings should be documented in the patient's medical records.

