7.2.5 Safety analyses

Adverse events will be coded using the Medical Dictionary for Drug Regulatory Activities (MedDRA). Standard BI summary tables and listings will be produced. All adverse events with an onset between start of treatment and end of the REP, as defined in [Section 1.2.](#), will be assigned to the on-treatment period for evaluation.

All treated patients will be included in the safety analysis. In general, safety analyses will be descriptive in nature and will be based on BI standards. No hypothesis testing is planned.

Statistical analysis and reporting of adverse events will concentrate on treatment-emergent adverse events, i.e. all adverse events occurring between start of treatment and end of the REP. Adverse events that start before first drug administration and deteriorate under treatment will also be considered as 'treatment-emergent'.

Frequency, severity, and causal relationship of adverse events will be tabulated by system organ class and preferred term after coding according to the current version of MedDRA at DBL.

Laboratory data will be analysed quantitatively and qualitatively. The latter will be done via comparison of laboratory data to their reference ranges. Values outside the reference range as well as values defined as clinically relevant will be summarised. Treatment arms will be compared descriptively with regard to distribution parameters as well as with regard to frequency and percentage of patients with abnormal values or clinically relevant abnormal values.

Vital signs, physical examinations, or other safety-relevant data observed at screening, baseline, during the course of the trial and at the end-of-trial evaluation will be assessed with regard to possible changes compared with findings before start of treatment.

Further details on the safety analysis will be specified in the TSAP.

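### SAP (Part 2) 7.8.2 moves coagulation tests, including fibrinogen, from safety to efficacy, so the visible safety section has no by-arm count below the protocol's 150 mg/dL threshold

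*SAP*

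**What the plan says.** **Protocol.** Section 5.2.3 introduces its table with "Safety laboratory parameters to be assessed are listed in" Table 5.2.3:1. That table has three blocks: haematology, clinical chemistry, and coagulation and inflammation. The third block holds fibrinogen, aPTT, prothrombin time or INR, antithrombin and anti-Xa. Section 7.2.5, on safety analyses, says of laboratory data: "Values outside the reference range as well as values defined as clinically relevant will be summarised".

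The protocol also sets a fibrinogen threshold. Section 1.4.2 states: "A plasma level of fibrinogen below 150 mg/dL has been associated with an elevated risk of bleeding". The same section names 100 mg/dL as a level below which bleeding risk rises. Section 1.4.3 says: "The bleeding risk is predicted from the plasma fibrinogen level".

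**SAP (Part 2).** Section 7.8.2 takes "Changes in coagulation and inflammatory markers on treatment", refers to Section 5.3 for their definition, and says: "They will be analysed in the efficacy section". It then writes "The following laboratory parameters are considered safety and hence processed according to standard safety processing rules" above a list that contains only haematology and clinical chemistry. For laboratory values, "frequency tables will be provided for the number of patients within and outside the reference range". The Part 1 SAP has the same rule in its own 7.8.2.

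**The concern.** Fibrinogen is the laboratory value on which the protocol's bleeding-safety argument rests. Section 4.1.2 bases dose selection on fibrinogen staying above 150 mg/dL. Sections 3.3.4.1 and 4.2.1 use the same level to interrupt and restart infusions. Amendment 3 lowered the fibrinogen entry requirement from the upper to the lower limit of normal and cited daily monitoring and the 150 mg/dL rule as justification. Section 1.1 reports that major bleeds to Day 6 in Part 1 occurred only in the alteplase groups.

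A reader of the Part 2 safety results will want to know how many patients in each arm went below that level, and whether they were the patients who bled. Followed as written, the visible safety plan does not produce that number. If it is produced at all, it will sit among the efficacy results and on a different analysis set.

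**Working it through.** No sample-size, power or error-rate figure is involved, so the check is a comparison of the texts.

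1. **Which tests are processed as safety?** Each test in protocol Table 5.2.3:1 was looked up in the safety list of SAP (Part 2) 7.8.2.

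| Block in protocol Table 5.2.3:1 | Tests in the protocol | Of these, on the SAP safety list |
|---|---|---|
| Haematology | 5 | 5 |
| Clinical chemistry | 14 | 14 |
| Coagulation and inflammation | 12 | 0 |

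   BNP or NT-proBNP counts as one test. The first two blocks are carried over in full and the third not at all. SAP 7.8.2 does not name fibrinogen or aPTT. That they belong to the markers sent to efficacy follows from the matching block title in the protocol and from their absence from the safety list.

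2. **On which patients?** SAP Table 6.3:1 puts further efficacy endpoints on the Full Analysis Set and all other safety analyses on the Treated Set. The first requires a post-baseline WHO scale assessment. The second requires, in the alteplase arm, at least one dose. The sets probably differ by few patients, but the Treated Set is the one on which major bleeding is analysed.

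3. **Is there a count at 150 mg/dL elsewhere in the visible safety section?** None was found.
   - The counts in 7.8.2 are against reference ranges. Protocol 5.2.3 says these are local, so they are not a fixed 150 mg/dL cut-off, even if they were applied to fibrinogen.
   - Protocol 7.2.5 mentions clinically relevant values, but no visible text defines that for fibrinogen.
   - SAP 7.8.1 names major bleeding, stroke, MI, PE, DVT, transient ischaemic attack and systemic embolism as events of interest. It names no laboratory threshold.

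4. **Is this only a version gap?** The Part 2 SAP is dated 26 October 2021 and rests on protocol Version 3. Amendment 3 is dated 17 February 2022. Its list of changes does not include protocol 5.2.3 or 7.2.5, so the mismatch does not arise from that amendment.

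5. **Are the data there?** The flow chart schedules fibrinogen at screening, on each of Days 1 to 7 and on Day 28. Days 1 to 7 fall inside the 288-hour on-treatment window of SAP 6.7. The schedule does not differ by arm. A lowest recorded value and a count per arm can therefore be derived without new sampling, assuming the scheduled values are entered in the trial database.

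**The case against.** The strongest reply is that SAP Section 5.3, which defines these marker endpoints, is not in the public text. It may specify lowest values, shift tables or a threshold count. That stands, and it limits the point: one cannot say that the plan has no such count anywhere. Whatever Section 5.3 contains, though, 7.8.2 places these markers in the efficacy section.

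Several stronger readings are tempting, and the documents do not support them.

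- A reader might infer that only average changes will be shown. The SAP's phrase names a topic and does not exclude other summaries.
- A reader might infer an undeclared departure from the protocol, since SAP section 4 does not list the move. Parts of the protocol's endpoint text are redacted and may already place coagulation changes among further endpoints.
- A reader might infer a broken promise. The visible protocol does not commit to a count below 150 mg/dL.
- A reader might try to size the problem from protocol 1.4.2, where fibrinogen falls to about 60% at 4 hours and generally recovers to more than 80% after 24 hours. By its title, the cited source is a healthy-volunteer study. The regimen here is a 14-hour infusion on Day 1 and 12 hours daily up to Day 5, and the documents give no baseline distribution. A low point at 4 hours could also be missed by roughly daily samples, so such an estimate would not measure what a new table recovers.

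There is also partial cover. SAP 7.8 says in general terms that safety is analysed as in the protocol, but the specific list in 7.8.2 is what would be programmed. Under protocol 5.2.3, abnormal values judged clinically relevant become adverse events, which depends on the investigator. Deviation C3.4 records a failure to interrupt the drug, not a threshold crossing, and has no counterpart in the SOC arm. None of these is a systematic count by arm.

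**Conclusion.** The concern holds as a mismatch in classification between protocol and SAP and as a gap in the visible safety reporting. The protocol treats the coagulation block as safety laboratory data, and the Part 2 SAP processes none of its 12 tests as safety. The visible safety section has no by-arm count at the protocol's own 150 mg/dL level.

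The conclusion rests on reading coagulation markers in SAP 7.8.2 as including fibrinogen, and on Section 5.3 not reversing the placement that 7.8.2 states. How many patients would be counted is unknown, and no figure should be attached. The confirmatory tests are unaffected, and nothing here bears on the dose or the interruption rules. The change is worth making before the Day 28 database snapshot. The SAP needs revision in any case, since it still uses the D-dimer strata that preceded Amendment 3.

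**What to change.** Reconcile SAP (Part 2) 7.8.2 with protocol 5.2.3 and 7.2.5.

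- Add the coagulation block to the safety laboratory list, on the Treated Set.
- For fibrinogen, report each patient's lowest recorded on-treatment value and the number and percentage of patients below 150 and below 100 mg/dL by arm. Present these descriptively and next to major bleeding events.
- State that counts from roughly daily samples are a lower bound on the number who crossed the threshold.
- Show aPTT and anti-Xa by type of heparin, and antithrombin where measured. Table 5.2.3:1 limits aPTT to patients on UFH, anti-Xa to those on LMWH, and antithrombin to sites where it is available. Protocol 4.2.1 and 4.2.2.1 apply different heparin policies in the two arms, so unstratified comparisons would mislead.
- Keep the efficacy-section analysis as an addition.

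The cost is a few extra descriptive tables from values already scheduled.

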7.8.3 Vital signs

The following vital signs will be descriptively analysed: systolic and diastolic blood pressure, body temperature, respiratory rate and pulse rate. Both absolute values and change from baseline are planned for this section of the report.

7.8.4 ECG

Not applicable.

7.8.5 Others

7.8.5.1 Pharmacokinetic analysis

Descriptive statistics of all PK parameters will be presented and will be performed on the PKS as outlined in [Section 6.3](#). In particular, the parameters / endpoints are:

- Css,1 (plasma concentration of alteplase at steady state of 2 hour infusion)
- Css,2 (plasma concentration of alteplase at steady state of long-term infusion)

Individual endogenous Tissue Plasminogen activator (TPA) will be determined for each patient at baseline using the first PK sample. Baseline levels will then be subtracted from all further concentration measurements (second and third samples), for each patient, in order to determine the Css,1 and Css,2 endpoints. In case the resulting concentration value is negative, it will then be set to “BLQ”.

As outlined in CTP Version 3 Section 7.2.4, a population PK analysis is planned to be conducted if sufficient data are available. The objectives of the population PK analysis are:-

- 1) to compare the alteplase concentrations in study 0135-0347 to PK simulations based on a previously developed population PK model for patients with acute myocardial infarction (AMI)
- 2) to derive model-based area under the curve (AUC) estimates for patients with ARDS based on the sparse PK measurements of study 0135-0347

Dataset preparation

Alteplase plasma concentrations, sampling times, infusion times, and covariates (e.g., age, weight, sex, and race) will be assembled and formatted for analysis. Detailed dataset specifications will be provided in a separate document.

Handling of missing data

Handling of missing data will be described in the dataset specification document.

Handling of outliers

Alteplase concentrations and covariate values will be included in the analysis whenever possible. However, for methods based on least-squares estimation and normal theory it is not good practice to include extreme values. Thus, outlying data points in the dependent variable may be excluded if they are infrequent, occur randomly and are spurious. Furthermore, it may be justified to exclude outlying individuals from model development. Also, extreme covariate values might be excluded. If more than 5% of alteplase plasma concentrations are excluded, a sensitivity analysis will be performed to evaluate the impact of the excluded data points on the final model. All outliers which are excluded from the analysis will be documented along with reasons for their exclusion.

Pharmacokinetic modeling strategy

In the following the framework of the PK modelling strategy is outlined, this may be adjusted as deemed necessary.

The pharmacokinetics of alteplase follows a 3-compartment distribution. A 3-compartment model cannot be developed using the information from study 0135-0347 alone as only sparse PK data is collected in a subset of the study population. Therefore, a previously developed population PK model for alteplase will be used to inform the current analysis. The population PK model for patients with AMI which is based on studies 0135.30 and 0135.53 is the preferred starting model. The pharmacokinetics of alteplase in these AMI studies were best described by a linear 3 compartment model. A baseline t-PA concentration was estimated to account for endogenous t-PA in plasma. Weight was included as covariate affecting baseline t-PA concentration and clearance of alteplase. Age was included as covariate affecting clearance of alteplase.

First, the alteplase plasma concentrations in study 0135-0347 will be compared to PK model simulations. Simulations will be performed using the previously developed population PK model for alteplase in patients with AMI. In the simulations, inter-individual and residual variability will be considered. The alteplase plasma concentration-time profiles will be simulated 1,000 times for each subject in study 0135-0347 assuming its actual infusion regimen, sampling scheme and weight. The simulated alteplase plasma concentrations at the different time points will be used to calculate the median concentration-time profile as well as its 90% prediction interval. This simulation results will be graphically compared to the observed data in study 0135-0347.

Given that the model-simulated plasma PK is in the same range as the observations, it will be further investigated whether the population PK model for patients with AMI can describe the individual alteplase concentrations in ARDS patients. Individual post-hoc estimates will be derived for study 0135-0347 using the parameters of the population PK model for patients with AMI. The distribution of the post-hoc estimates around the typical parameters and the description of the individual plasma concentrations will be investigated.

Provided that the population PK model for patients with AMI successfully describes the individual profiles of patients with ARDS, the individual PK parameters will be determined. In addition, AUC will be derived within NONMEM® from the individual PK parameters considering the patients' actual alteplase doses, infusion regimen, and covariates. In case, the structural PK model of patients with AMI cannot describe the PK of patients with ARDS, necessary adjustments (e.g. re-estimation of clearance) might be implemented into the model.

The population PK model for patients with AMI comprises the impact of weight and age on the PK of alteplase. Assessment of any remaining trends for weight, age, sex, and race will be conducted e.g. by graphical inspection plotting empirical Bayes estimate versus covariate values and conditional weighted residuals (CWRES) versus covariate values.

Inter-subject variability will be modeled using exponential random effect models. Residual variability will be modeled starting with the same error model structure as in patients with

AMI; adjustments will be made if necessary. The set of inter individual (η) and residual (ϵ) variability values are assumed to be symmetrically distributed around 0 with variances ω^2 and σ^2 , respectively.

Evaluation

If model development is necessary, objective function values (for nested models) as well as the criteria listed below will be considered:

- A “successful minimization” statement by the NONMEM® program at the end of the estimation step.
- The final parameter estimates have a number of significant digits of 3 for all θ ’s.
- Estimates of θ ’s not close to a boundary.
- Correlation of the uncertainty of the estimates of fixed effect parameters < 0.95 or >-0.95.
- No significant trends in the basic goodness-of-fit plots (predictions (PRED), individual predictions (IPRED) vs. DV)
- Residuals (CWRES) scatter randomly and uniformly around zero when plotted against population prediction and time.
- ETAs are normally distributed around 0.
- No significant model misspecification in the individual predicted concentration-time profiles when compared to the observed profiles.

If a model is accepted as final model, although one or more of the criteria above are not fulfilled, the reasons for its acceptance need to be given in the report.

If model development is necessary, the final model will be evaluated using a prediction corrected visual predictive check (pcVPC, [13](#)). A visual predictive check shows the ability of the model to simulate data that are similar to the observed data that were used for model development. The concentration-time profiles will be simulated 1,000 times using the same actual doses, infusion regimen, subjects’ covariates, and study design as in the analysis data set. In order to adjust for the differences in e.g. actual doses, a pcVPC will be performed in which the observed and simulated DV will be normalized based on the typical population prediction.

